7. ADVERSE EVENTS: LIST AND REPORTING REQUIREMENTS

Adverse event (AE) monitoring and reporting is a routine part of every clinical trial. The following list of AEs (Section 7.1) and the characteristics of an observed AE (Section 7.2) will determine whether the event requires expedited reporting in addition to routine reporting.

7.1 Adverse Event and Laboratory Abnormalities

7.1.1 Clinical AE's

7.1.1.1 Definition of Adverse Events

Per the International Conference of Harmonization (ICH), an AE is any untoward medical occurrence in a patient or clinical investigation subject administered a pharmaceutical product and which does not necessarily have a causal relationship with the treatment. An AE can therefore be any unfavorable and unintended sign (including an abnormal laboratory finding), symptom, or disease temporally associated with the use of a medicinal (investigational) product, whether or not considered related to the medicinal (investigational) product. Pre-existing conditions which worsen during a study are to be reported as AEs.

7.1.1.2 CTCAE term (AE description)

The descriptions found in the revised NCI Common Terminology Criteria for Adverse Events (CTCAE) version 5.0 will be utilized for AE reporting. All appropriate treatment areas should have access to a

Confidential
copy of the CTCAE version 5.0. A copy of the CTCAE version 5.0 can be downloaded from the CTEP web site (<http://ctep.cancer.gov>).

7.1.1.3 Severity

Severity of all adverse events will be graded according to the NCI Common Terminology Criteria for Adverse Events v 5.0 (CTCAE) on a five-point scale (grades 1 to 5) and reported in detail on the CRF.
Adverse events not listed on the CTCAE should be graded as follows:

CTC Grade	Equivalent To:	Definition
Grade 1	Mild	Discomfort noticed but no disruption of normal daily activity
Grade 2	Moderate	Discomfort sufficient to reduce or affect daily activity; no treatment or medical intervention is indicated although this could improve the overall well-being or symptoms of the patient
Grade 3	Severe	Inability to work or perform normal daily activity; treatment or medical intervention is indicated in order to improve the overall well-being or symptoms; delaying the onset of treatment is not putting the survival of the patient at direct risk.
Grade 4	Life threatening/ disabling	An immediate threat to life or leading to a permanent mental or physical conditions that prevents work or performing normal daily activities; treatment or medical intervention is required in order to maintain survival.
Grade 5	Death	AE resulting in death

7.1.1.4 Drug-Adverse Event relationship

The causality relationship of study drug to the adverse event will be assessed by the investigator as either:

Yes or No

If there is a reasonable suspected causal relationship to the study medication, i.e. there are facts (evidence) or arguments to suggest a causal relationship, drug-event relationship should be assessed as **Yes**.

The following criteria should be considered in order to assess the relationship as Yes:

- Reasonable temporal association with drug administration
- Known response pattern to suspected drug
- Disappears or decreases on cessation or reduction in dose
- Reappears on rechallenge

The following criteria should be considered in order to assess the relationship as No:

- It does not follow a reasonable temporal sequence from administration of the drug.
- It may readily have been produced by the subject's clinical state, environmental or toxic factors, or other modes of therapy administered to the subject.
- It does not follow a known pattern of response to the suspected drug.
- It does not reappear or worsen when the drug is readministered.

7.1.1.5 Definition of Serious Adverse Events

A serious adverse event is any experience that suggests a significant hazard, contraindication, side effect or precaution. It is any Adverse Event that at any dose fulfils at least one of the following criteria:

- is fatal; (results in death; NOTE: death is an outcome, not an event)
- is Life-Threatening (NOTE: the term "Life-Threatening" refers to an event in which the patient was at immediate risk of death at the time of the event; it does not refer to an event which could hypothetically have caused a death had it been more severe).
- required in-patient hospitalization or prolongation of existing hospitalization;
- results in persistent or significant disability/incapacity;
- is a congenital anomaly/birth defect;
- is medically significant or requires intervention to prevent one or other of the outcomes listed above

7.1.1.6 Progression of Underlying Malignancy

Progression of underlying malignancy is not reported as an adverse event if it is clearly consistent with the suspected progression of the underlying cancer as defined by WHO criteria, or other criteria as determined by protocol. Hospitalization due solely to the progression of underlying malignancy should NOT be reported as a serious adverse event. Clinical symptoms of progression may be reported as adverse events if the

Confidential

symptom cannot be determined as exclusively due to the progression of the underlying malignancy or does not fit the expected pattern of progression for the disease under study.

Symptomatic deterioration may occur in some patients. In this situation, progression is evident in the patient's clinical symptoms, but is not supported by the tumor measurements. Or the disease progression is so evident that the investigator may elect not to perform further disease assessments. In such cases, the determination of clinical progression is based on symptomatic deterioration. These determinations should be a rare exception as every effort should be made to document the objective progression of underlying malignancy.

If there is any uncertainty about an adverse event being due only to the disease under study, it should be reported as an AE or SAE.

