11.1.4.3 Evaluation of Best Overall Response

The best overall response is the best response recorded from the start of the treatment until disease progression/recurrence (taking as reference for progressive disease the smallest measurements recorded since the treatment started). The patient's best response assignment will depend on the achievement of both measurement and confirmation criteria.

For Patients with Measurable Disease (*i.e.*, Target Disease)

Target Lesions	Non-Target Lesions	New Lesions	Overall Response	Best Overall Response when Confirmation is Required*
CR	CR	No	CR	≥4 wks. Confirmation**
CR	Non-CR/Non-PD	No	PR	≥4 wks. Confirmation**
CR	Not evaluated	No	PR	
PR	Non-CR/Non-PD/not evaluated	No	PR	
SD	Non-CR/Non-PD/not evaluated	No	SD	Documented at least once ≥4 wks. from baseline**
PD	Any	Yes or No	PD	no prior SD, PR or CR
Any	PD***	Yes or No	PD	
Any	Any	Yes	PD	

* See RECIST 1.1 manuscript for further details on what is evidence of a new lesion.
** Only for non-randomized trials with response as primary endpoint.
*** In exceptional circumstances, unequivocal progression in non-target lesions may be accepted as disease progression.

Note: Patients with a global deterioration of health status requiring discontinuation of treatment without objective evidence of disease progression at that time should be reported as “*symptomatic deterioration*.” Every effort should be made to document the objective progression even after discontinuation of treatment.

For Patients with Non-Measurable Disease (*i.e.*, Non-Target Disease)

Non-Target Lesions	New Lesions	Overall Response
CR	No	CR
Non-CR/non-PD	No	Non-CR/non-PD*
Not all evaluated	No	not evaluated
Unequivocal PD	Yes or No	PD
Any	Yes	PD

* 'Non-CR/non-PD' is preferred over 'stable disease' for non-target disease since SD is increasingly used as an endpoint for assessment of efficacy in some trials so to assign this category when no lesions can be measured is not advised

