11.1.7 Progression-Free Survival

PFS is defined as the duration of time from start of treatment to time of progression or death, whichever occurs first.

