13. STATISTICAL CONSIDERATIONS

13.1 Study Design/Endpoints

This will be a multi-center open label phase II study of tebentafusp in patients with unresectable or metastatic CCS. CCS is an orphan disease with few efficacious systemic

treatment options and few standard of care treatment options in the unresectable or metastatic setting. This study will assess for a signal of efficacy of a novel immunotherapeutic agent (tebentafusp) in the HLA-A*02:01-positive patients and simultaneously prospectively measure real-world outcomes in the HLA-A*02:01-negative patients.

The primary endpoint is to estimate PFS rate at 24 weeks, as determined by RECIST 1.1. In the CREATE trial (one of the few prospective clinical trials in this disease), the PFS rate at 6 months (PFS₆) for patients with advanced CCS treated with crizotinib was approximately 25%.⁹ In other prospective and retrospective studies of alternative systemic therapies, the median PFS was between 2 and 3 months and the PFS₆ was not reported.^{6,8,32}

Van Glabbeke and colleagues³³ have previously described appropriate thresholds for PFS₆ in the design of phase II studies in soft tissue sarcoma patients refractory to first-line treatment. Based on historical controls, they conclude a PFS₆ of 8% is not promising and PFS₆ of 14% to be promising.³³ Based on all of the above, we believe PFS₆ is an appropriate and meaningful clinical endpoint in this patient population. We will consider a 10% PFS₆ as not promising and 30% to be promising.

Simon's two-stage minimax design³⁴ will be used. The null hypothesis that the true PFS rate at 24 weeks is 10% will be tested against a one-sided alternative that it is 30%. In the first stage, 13 patients will be accrued. If ≤ 1 of the first 13 patients enrolled is progression-free at 24 weeks, the protocol will stop enrolling patients due to futility. Otherwise, 10 additional patients will be accrued for a total of 23 patients treated. The study will be claimed positive if 5 or more of 23 patients are progression-free at 24 weeks. This design yields a one-sided type I error rate of 0.1 and power of 0.84.

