All patients who have received at least one dose of study therapy will be assessable for safety. Patients evaluable for efficacy analysis will include all patients treated with tebentafusp who are assessable for response. Patients who have no assessment of response post-baseline will not be considered evaluable for response unless they missed the assessment due to progression of disease or death, in which case they will be considered non-responders for that time point. Patients with at least one post-baseline assessment who are not assessed at 24 weeks for reasons other than progression of disease, death, will be evaluated based on their last imaging assessment. For example, patients with excessive toxicity will be censored at the date of their most recent disease evaluation prior to receiving any future systemic treatment regimens. Patients who are not evaluable (excluding those who died, had progression of disease, stopped study treatment due to treatment-related toxicity, or those with at least one post-baseline assessment) may be replaced.

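### Section 13.1 does not say whether a patient who stops for tumour-related deterioration without RECIST progression counts as progression-free at 24 weeks

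*Protocol*

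**What the plan says.** Four places in the protocol bear on this.

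- **Section 13.1, endpoint.** "The primary endpoint is to estimate PFS rate at 24 weeks, as determined by RECIST 1.1".
- **Section 13.1, missing 24-week assessment.** Among patients scanned at least once after baseline, those "who are not assessed at 24 weeks for reasons other than progression of disease, death, will be evaluated based on their last imaging assessment". The exception for progression is not tied to RECIST PD.
- **Section 11.1.7.** "PFS is defined as the duration of time from start of treatment to time of progression or death, whichever occurs first". This sentence names no criterion for progression.
- **Section 11.1.4.3.** Patients whose general health declines so far that treatment must stop, "without objective evidence of disease progression at that time should be reported as" symptomatic deterioration. That is a label of its own, not PD. The note adds: "Every effort should be made to document the objective progression even after discontinuation of treatment".

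Section 7.1.1.6, on adverse-event reporting, describes patients whose symptoms show progression that the measurements do not support, and patients whose progression is so plain that the investigator omits further disease assessments. It says "In such cases, the determination of clinical progression is based on symptomatic deterioration", and then limits this: "These determinations should be a rare exception as every effort should be made to document the objective progression of underlying malignancy".

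**The concern.** Take a patient with stable disease at week 6 or 12 who then stops because of tumour-related decline. No later scan shows PD, and the patient is alive at week 24. Two outcomes can be read from Section 13.1:

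- If progression of disease includes clinical progression, the 24-week assessment was missed because of progression. The last-imaging rule does not apply, and the patient is most naturally a failure.
- If progression of disease means RECIST PD only, the patient has not progressed. The last stable scan governs, and the patient is scored progression-free at 24 weeks.

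The second reading records a success for a patient who is doing badly, so the error runs in one direction: it raises the primary rate. The decision cut-offs are small (stop at 1 or fewer of 13, positive at 5 or more of 23), so one such patient can change the futility decision or the final claim.

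**Working it through.** **Inputs (Section 13.1).** Stage 1 has 13 patients and stops if 1 or fewer are progression-free. Stage 2 adds 10, and the trial is positive if 5 or more of 23 are progression-free. The null rate is 10% and the alternative 30%. Stated: one-sided type I error 0.1 and power 0.84.

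**Step 1: reproduce the design.** The probability of a positive trial at true rate p is

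R(p) = Σ (x = 2 to 13) P(X₁ = x) · P(X₂ ≥ 5 − x), with X₁ ~ Bin(13, p) and X₂ ~ Bin(10, p).

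At p = 0.10 the terms are:

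| x | P(X₁ = x) | P(X₂ ≥ 5 − x) | Product |
|---|---|---|---|
| 2 | 0.2448 | 0.0702 | 0.0172 |
| 3 | 0.0997 | 0.2639 | 0.0263 |
| 4 | 0.0277 | 0.6513 | 0.0180 |
| 5 or more | 0.0065 | 1 | 0.0065 |

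The sum is R(0.10) = 0.068, and R(0.30) = 0.844. The stated power reproduces. The stated 0.1 fits as the nominal ceiling; the attained level is 0.068. The chance of stopping at stage 1 under the null is P(X₁ ≤ 1) = 0.621.

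**Step 2: a share of true failures scored as successes.** The protocol gives no frequency, so the share q is an assumption. If q of the true failures take this path and are scored on a stable scan, the apparent rate is p′ = 0.10 + 0.90q. The expected number of such patients is 23 × 0.90 × q.

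| q (assumed) | Expected patients of 23 | p′ | Type I error R(p′) |
|---|---|---|---|
| 0 | 0 | 0.100 | 0.068 |
| 1% | 0.21 | 0.109 | 0.091 |
| 2% | 0.41 | 0.118 | 0.118 |
| 5% | 1.04 | 0.145 | 0.219 |
| 10% | 2.07 | 0.190 | 0.428 |

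At 1% the error stays below the stated 0.1; at 2% it is above.

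**Step 3: exactly one such patient.** Fix one patient as a success and let the other 22 have a true rate of 10%.

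- In stage 1, the other 12 need at least 1 success and the other 22 need at least 4 in total: Σ (x = 1 to 12) P(Bin(12, 0.1) = x) · P(Bin(10, 0.1) ≥ 4 − x) = 0.168.
- In stage 2, the 13 need at least 2 and the other 22 need at least 4 in total: Σ (x = 2 to 13) P(Bin(13, 0.1) = x) · P(Bin(9, 0.1) ≥ 4 − x) = 0.150.

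**Step 4: does the schedule close the gap?** Section 5.3 says patients who stop treatment are not withdrawn and should return for assessments. However, the end-of-treatment list in Section 10.3 has no imaging, the Study Calendar marks no radiographic evaluation at end of treatment or follow-up, and Section 10.3 describes the later follow-up as survival only. The request to document objective progression is therefore not backed by a scheduled scan.

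**The case against.** A reader might infer that Sections 7.1.1.6 and 11.1.4.3 contradict each other, with the first making clinical progression a PFS event. The text does not support that. Section 7.1.1.6 decides what is reported as an adverse event and defines no efficacy event. Both sections use the term symptomatic deterioration, and both ask for every effort to document objective progression. The endpoint is tied to RECIST 1.1 in the Synopsis and in Sections 1.1 and 13.1. What is open is the last-imaging rule in 13.1, helped by the unqualified PFS definition in 11.1.7.

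Three further points on the other side stand:

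- **The natural reading of 13.1 already makes some of these patients failures.** A scan omitted because progression was evident was arguably missed because of progression. The success route needs the RECIST-only reading.
- **The case is narrow.** It needs a stable post-baseline scan, a stop for symptoms, no later scan showing PD, and survival to week 24. Section 7.1.1.6 calls such determinations a rare exception. The short median PFS figures in the protocol show that progression is fast; they do not show that it goes undocumented.
- **An effect on the clinical benefit rate is not shown.** Best overall response is the best recorded before progression, so stable disease at week 6 stays stable disease. The Synopsis definition requires at least 6 months, which a week-6 or week-12 scan does not document.

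One reply does not help the plan. If the RECIST-only endpoint is taken to settle the question, it leads to the less favourable result: the patient is scored progression-free at week 24 on an early scan.

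**Conclusion.** The concern holds in a limited form. Section 13.1 leaves open how the binary 24-week endpoint treats a patient who stops for tumour-related deterioration without RECIST PD, and one of the two readings biases the primary rate upward. The protocol does not say that such patients are successes, nor that they are common.

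The size depends on an unknown frequency. Type I error runs from 0.091 to 0.428 for assumed shares of 1% to 10% of true failures, and is 0.150 to 0.168 if exactly one patient is affected, against 0.068 with none. These figures assume that every such patient is scored as a success and that the true rate is 10%. Even a rare path matters when one patient can decide 1 of 13 or 5 of 23, so the text should be settled before the stage 1 decision.

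**What to change.** - **Section 13.1.** State that a patient who stops for symptomatic deterioration attributed to the tumour, and has no scan at or after 24 weeks showing absence of progression, is counted as not progression-free at 24 weeks. State that the last-imaging rule does not apply to this patient.
- **Section 11.1.7.** Name RECIST 1.1 progression or death as the main PFS event. Add a sensitivity analysis that counts clinical progression as an event on its date. Making clinical progression the main time-to-event definition would depart from the RECIST 1.1 endpoint and add an investigator's judgement in an open-label trial, so it belongs in the sensitivity analysis.

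The cost is a few sentences and one extra analysis. The reported 24-week rate may be slightly lower, and attributing deterioration to the tumour is partly a judgement. The change concerns scoring only and leaves treatment decisions as they are.

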7.1.2 Treatment and Follow-up AEs

After the discontinuation of therapy, continue to follow up AEs as follows:

Related AEs: Follow until one of the following occurs:

- Resolved or improved to baseline
- Relationship is reassessed as unrelated
- Death
- Start of new anti-cancer regimen
- Investigator confirms that no further improvement can be expected
- Clinical or safety data will no longer be collected, or final database closure

Unrelated severe or life threatening AEs: Follow until one of the following occurs:

- Resolved or improved to baseline
- Severity improved to grade 2
- Death
- Start of new anti-cancer regimen
- Investigator confirms that no further improvement can be expected
- Clinical or safety data will no longer be collected, or final database closure

Unrelated Grade 1 or Grade 2 AEs: Follow as clinically indicated.

The final outcome of each adverse event must be recorded on the CRF

7.1.3 Laboratory Test Abnormalities

Confidential

Laboratory test results will be recorded on the laboratory results pages of the CRF, or appear on electronically produced laboratory reports submitted directly from the central laboratory, if applicable.

Any laboratory result abnormality fulfilling the criteria for a serious adverse event (SAE) should be reported as such.

Any treatment-emergent abnormal laboratory result which is clinically significant, i.e., meeting one or more of the following conditions, should be recorded on the adverse event page in the CRF:

- Accompanied by clinical symptoms
- Leading to a change in study medication (e.g. dose modification, interruption or permanent discontinuation)
- Requiring a change in concomitant therapy (e.g. addition of, interruption of, discontinuation of, or any other change in a concomitant medication, therapy or treatment)

7.1.4 Follow-up of Abnormal Laboratory Test

In the event of medically significant unexplained abnormal laboratory test values, the test should be repeated and followed until it has returned to the normal range, baseline value and/or an adequate explanation of the abnormality is found. If a clear explanation is established it should be recorded in the CRF.

7.2 Handling of Safety Parameters

7.2.1 Reporting of Adverse Events

All adverse events (related and unrelated) occurring during the study and up to 30 days after the last dose of study medication must be reported. Reporting the specific time of onset of a given AE is only necessary when it occurs in relation to study drug administration.

7.2.2 Reporting of Serious Adverse Events (immediately reportable)

Any clinical adverse event or abnormal laboratory test value that is *serious* and which occurs during the course of the study (as defined in section 7.2.1.5 above), must be reported to the Principal Investigator(s), SARC and Immunocore **within one working day** of the investigator becoming aware of the event (expedited reporting). If only limited information is initially available, follow-up reports are required. The original SAE Form must be kept on file at the study site.

SAE's must be reported on the MedWatch Form 3500A along with the completed SAE Coversheet (operations manual) and emailed to [name] and [contact].

Related Serious Adverse Events **MUST** be collected and reported regardless of the time elapsed from the last study drug administration, even if the study has been closed.

Unrelated Serious Adverse Events must be collected and reported during the study and for up to 30 days after the last dose of study medication.

7.2.3 Pregnancy

Females must be instructed to stop taking the study medication and immediately inform the investigator if pregnancy occurs during the study. Pregnancies occurring up to 6 months after the completion of the study medication must also be reported to the investigator. The investigator should report all pregnancies within 24 hours to the sponsor.

The investigator should counsel the patient; discuss the risks of continuing with the pregnancy and the possible effects on the fetus. Monitoring of the patient should continue until conclusion of the pregnancy.

Pregnancy occurring in the partner of a male patient participating in the study should also be reported to the investigator and the sponsor. The partner should be counseled and followed as described above.

Women of childbearing potential, defined as all women physiologically capable of becoming pregnant, can be included in the study provided they are using highly effective methods of contraception during dosing and for 6 months after the last dose of tebentafusp or Investigator's Choice.

Highly effective contraception methods include the following:

- Total abstinence from sexual relations for the duration of the treatment when applicable to the lifestyle of the patient. Periodic abstinence (eg, calendar, ovulation, symptothermal, post-ovulation methods) and withdrawal are not acceptable methods of contraception.
- Female sterilization (have had surgical bilateral oophorectomy with or without hysterectomy) or tubal ligation at least 6 weeks before taking study treatment. In case of oophorectomy alone, this applies only when the reproductive status of the woman has been confirmed by follow-up hormone level assessment.
- Male sterilization (at least 6 months prior to Screening). For female patients on the study, the vasectomized male partner should be the sole partner for that patient.
- The combination of any 2 of the following methods when both are used simultaneously:
 - Use of oral, injected, or implanted hormonal methods of contraception or other forms of hormonal contraception that have comparable efficacy (failure rate < 1%), for example hormone vaginal ring or transdermal hormone contraception

- Placement of an intrauterine device or intrauterine system
- Barrier methods of contraception: condom or occlusive cap (diaphragm or cervical/vault caps) when used with spermicidal foam, gel, film, cream, or used of a spermicidal vaginal suppository

In case of use of oral contraception, women should have been stable on the same oral contraceptive pill for a minimum of 3 months before beginning treatment on this study.

Women are considered post-menopausal and not of childbearing potential if they have had 12 months of natural (spontaneous) amenorrhea with an appropriate clinical profile (eg, age appropriate, history of vasomotor symptoms), or have had surgical bilateral oophorectomy (with or without hysterectomy) or tubal ligation at least 6 weeks prior to study treatment. In the case of oophorectomy alone, only when the reproductive status of the woman has been confirmed by follow-up hormone level assessment is she considered not of childbearing potential.

